5.2. Analysis of baseline data

The definition of baseline will be dependent on the analysis performed and the cohort of patients utilized. The following are the various definitions of baseline that may be used in the analyses:

5.2.1. 205MS301-205MS303 Study Baselines

205MS301 Baseline

Study 205MS301 Baseline is defined as the latest available value prior to or on the date of the first dose of study treatment in Study 205MS301.

205MS303 Baseline

Study 205MS303 Baseline is defined as the latest available value prior to or on the date of the first dose of study treatment in Study 205MS303.

Demographic characteristics, baseline disease characteristics and medical history will be summarized using the 205MS301-303 ITT population at the 205MS301 Baseline and at the 205MS303 Baseline.

DAC HYP Baseline

DAC HYP Baseline is equal to the 205MS301 baseline for subjects randomized to DAC HYP in 205MS301, or the 205MS303 baseline for subjects randomized to IFN β -1a in 205MS301. If no assessments, or if multiple measurements were performed on the day of first dose of DAC HYP, the last measurement prior to the first dose of DAC HYP will be used.

Unless otherwise specified, the DAC HYP Baseline will be utilized in measurements for safety assessments such as laboratory values and vital signs.

5.2.2. 205MS203-205MS303 Study Baselines

205MS303 Baseline is defined as the latest available value prior to or on the date of the first dose of study treatment in Study 205MS303.

DAC HYP Baseline

Subjects enrolled from 205MS203 study had completed the 205MS201, 205MS202, and 205MS203 studies. For subjects randomized to DAC HYP either 150 mg or 300 mg in 205MS201, the DAC HYP Baseline is defined as the 205MS201 baseline. For subjects randomized to placebo in 205MS201, the DAC HYP Baseline is defined as the 205MS202 Baseline. If no assessments, or if multiple measurements were performed on the day of first dose of DAC HYP, the last measurement prior to the first dose of DAC HYP will be used.

	Protocol 205MS303 Statistical Analysis Plan	Final Version 1.0
---	--	--------------------------

5.2.3. 205MS302-205MS303 Study Baselines

205MS303 Baseline

Study 205MS303 Baseline is defined as the latest available value prior to or on the date of the first dose of study treatment in Study 205MS303.

DAC HYP Baseline

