5.4. General Methods of Analysis

For the 205MS301-303 ITT population, efficacy analyses will focus on data from the 205MS303 treatment period but will include some additional analyses across the combined study period. In general, summary statistics will be presented by previous treatment group of the 205MS301 study (IFN β -1a 30 μ g and 150 mg DAC HYP). Safety analyses will include subjects in the 205MS301-303 Safety Population and use the data from the 205MS303 Treatment period only. Analyses will be presented by previous treatment group of the 205MS301 study (IFN β -1a 30 μ g and 150 mg DAC HYP) and for all subjects combined.

For the 205MS203-303 ITT population, efficacy analyses will focus on data from the 205MS303 treatment period. Summary statistics will be summarized for all subjects combined. Safety analyses will include the data from the 205MS303 Treatment period, and will be presented for all subjects combined. Note that subjects enrolled from the 205MS203 study may receive DAC HYP at a higher dose (300 mg) during the 205MS201 and/or 205MS202 studies. Given the long duration time since last exposure to high dose of DAC HYP and to be consistent with the analyses in the 205MS203 clinical study report, analyses will not be presented by high/low dose level in previous studies.

For the 205MS302-303 ITT population, efficacy and safety analyses will focus on subject data from the 205MS303 treatment period, and will be presented for all subjects combined.

Analyses will generally be descriptive in nature. For relevant efficacy analyses, confidence intervals will be provided for each treatment group where appropriate to characterize the variability around the point estimates. Statistical hypothesis testing may be completed for selected analyses [REDACTED]

Visit Windows

For by-visit analyses, visit windows will be utilized. Data will be windowed to the nearest scheduled visit. If two or more evaluations occur in the same visit window, the evaluation measured on a day closest to the target visit day will be selected for inclusion in the analysis. If multiple evaluations are equally close to the target visit day, then the evaluation with an earliest day will be selected for inclusion in the analysis. If several samples are collected on the same day but at different times, the earliest time will be used.

Missing measurements

In general, no imputation for missing measurements will be performed, unless specified otherwise.

Missing dates

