7.11. Symbol Digit Modalities Test (SDMT)

For the 205MS301-303 ITT population, SDMT actual value and change from 205MS301 baseline will be summarized by 205MS301 treatment group in the Combined Study Period (by study visit in 205MS301 and 205MS303 studies). Additionally, proportion of patients with ≥ 3 points or ≥ 4 points increase from 205MS301 baseline, and proportion of patients with ≥ 3 points or ≥ 4 points decrease from 205MS301 baseline will be summarized by 205MS301 treatment group in the Combined Study Period (see also, Benedict et. al 2017). Similar analyses will be done for the 205MS303 treatment period with changes from 205MS303 baseline. Note that in the 205MS303 study, SDMT is only collected for subjects in 205MS301-303 ITT population starting from week 144 in the study.

SDMT is not collected for patients enrolled from the 205MS203 or 205MS302 study to the 205MS303 study.

7.12. 3 Second Paced Auditory Serial Addition Test (PASAT3)

For the 205MS301-303 ITT population, PASAT3 actual value and change from 205MS301 baseline will be summarized by 205MS301 treatment group in the Combined Study Period (by study visit in 205MS301 and 205MS303 studies). Similar analyses will be done for the 205MS303 treatment period with changes from 205MS303 baseline.

Note that PASAT3 is not collected for patients enrolled from the 205MS203 or 205MS302 study to the 205MS303 study.

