For missing baseline and post-baseline values, if a subject is missing only one trial for any post-baseline visit, then the score from the non-missing trial will be used to calculate both the Z-score and Raw score, unless the reason for the missing score is due to MS related physical limitation or other physical limitations. If reason is due to one of the reasons listed above, the score for that specific trial will be back-calculated using the Z-score value of -13.7 (see formula below), and then the average of the two trials will be taken. The steps outlined above will remain the same.

If both scores from the two trials are missing for any post-baseline visit due to MS related physical limitation or other physical limitations, (based on the missing data algorithm suggested by the MSFC algorithm) the subject will be given a Z-score of -13.7 for the Timed 25-Foot walk. The Row-score will be back-calculated using the following formula:

	
Protocol 205MS303 Statistical Analysis Plan
	
Final Version 1.0

---	--	---

$$R_{25\text{-foot-walk}} = MEAN(reference) + 13.7 * SD(reference).$$

9HPT Z-score Calculation

Z-score for the 9HPT is calculated as in the following formula:

$$Z_{9HPT} = \frac{\left(\left(\frac{1}{(t_{11}+t_{12})/2} + \frac{1}{(t_{21}+t_{22})/2} \right) / 2 \right) - MEAN(reference)}{SD(reference)},$$

where t_{11} , t_{12} , t_{21} , t_{22} are the time (in seconds) taken to complete for dominant hand trial 1, dominant hand trial 2, non-dominant hand trial 1, and non-dominant hand trial 2, respectively. The mean (reference) and SD (reference) are the mean and standard deviation, respectively, of reference population's baseline score.

9HPT Raw Score Calculation

Raw-score for the 9HPT is calculated as in the following formula:

$$R_{9HPT} = \left((t_{11} + t_{12}) / 2 + (t_{21} + t_{22}) / 2 \right) / 2$$

where t_{11} , t_{12} , t_{21} , t_{22} are the time (in seconds) taken to complete for dominant hand trial 1, dominant hand trial 2, non-dominant hand trial 1, and non-dominant hand trial 2, respectively.

Missing Values for 9-hole Peg Test

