For missing baseline and post-baseline values, if a subject is missing only one trial for any post-baseline visit (for either dominant or non-dominant hand), then the score from the non-missing trial will be used to calculate both scores, unless the reason for the missing score is due to MS related physical limitation or other physical limitations. If reason is due to one of the reasons listed above, the score for that specific trial will be imputed with a raw score value of 777, and then the average of the two trials will be taken. The steps outlined above will remain the same.

The missing data algorithm suggested by the MSFC manual will be used to impute missing values. If both scores from either hands are missing for any post-baseline visit, due to MS related physical limitation or other physical limitations, then the subject will be given a Row-score using a value of 777. The Z-score will be calculated with the following formula:

$$Z_{9\text{HPT}} = \frac{\frac{1}{777} - \text{MEAN}(\text{reference})}{\text{SD}(\text{reference})},$$

PASAT 3 Z-score Calculation

For the PASAT 3, the z-score for each subject at each time-point will be created by subtracting the reference population's baseline mean score on the PASAT 3 from the subject's PASAT 3 score and dividing by the baseline SD on the PASAT 3 of the reference population, i.e.

$$Z_{\text{PASAT3}} = \frac{\text{PASAT 3 raw score} - \text{MEAN}(\text{reference})}{\text{SD}(\text{reference})},$$

and PASAT 3 raw score = # of items correct.

Missing Values

For missing post-baseline values, if a subject is missing the PASAT 3 score due to MS disease limitations, then a score of 0 will be imputed as the *raw score*. Missing baseline values will not be imputed.

For the 205MS301-303 ITT population, actual value, change and percentage change from the 205MS301 baseline in the MSFC z-scores as well as for each individual MSFC component z-scores will be summarized by 205MS301 treatment group in Combined Study Period (by study visit in 205MS301 and 205MS303 studies). Similarly, for the 205MS301-303 ITT population, the MSFC z-scores as well as for each individual MSFC component z-scores with change from 205MS303 baseline will be summarized by 205MS301 treatment group in the 205MS303 Treatment Period (by study visit in 205MS303 study).

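### SAP 8.4.3 gives disability-related inability the worst MSFC score only after baseline and does not say how inability at the 205MS303 entry test is scored, so loss before entry can be counted as 205MS303 decline

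*SAP*

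**What the plan says.** **Worst-score rules (SAP 8.4.3).**
- PASAT 3: "For missing post-baseline values, if a subject is missing the PASAT 3 score due to MS disease limitations, then a score of 0" is imputed as the raw score. The next sentence reads "Missing baseline values will not be imputed".
- Timed 25-Foot Walk, both trials missing: the condition is "If both scores from the two trials are missing for any post-baseline visit due to MS related physical limitation or other physical limitations", and then "the subject will be given a Z-score of -13.7 for the Timed 25-Foot walk".
- 9HPT, both trials missing: a raw score of 777, again conditioned on post-baseline visits.
- Walk and 9HPT, one trial missing: both rules open "For missing baseline and post-baseline values, if a subject is missing only one trial for any post-baseline visit". The lead-in names baseline and the condition excludes it.

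**Baselines and analyses.** SAP 5.2.1 has the 205MS303 baseline "defined as the latest available value prior to or on the date of the first dose of study treatment in Study 205MS303". Footnote 3 to Table 1 lets a test from the last 205MS301 visit serve as that baseline if it was within 28 days of the first 205MS303 dose. SAP 8.4.3 and Table 8 summarise MSFC and component z-scores twice: as change from the 205MS301 baseline over the Combined Study Period, and as change from the 205MS303 baseline over the 205MS303 Treatment Period.

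**PASAT 3 on its own (SAP 7.12).** "PASAT3 actual value and change from 205MS301 baseline will be summarized by 205MS301 treatment group in the Combined Study Period", with a similar analysis from the 205MS303 baseline. Section 7.12 has no missing-data rule. The general default in 5.4 is "In general, no imputation for missing measurements will be performed, unless specified otherwise".

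**The concern.** The 205MS303 entry test has two roles. Relative to the 205MS301 baseline it is a post-baseline visit, where inability is scored at the worst value. Relative to the 205MS303 Treatment Period it is the baseline, where 8.4.3 gives PASAT 3 no score and gives the walk and 9HPT no clear rule. The word baseline in 8.4.3 is not tied to either role.

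Take a subject who could not do a component at entry and is unchanged at Week 12. If the entry inability has no score, the latest available value is an earlier, better one. The Week 12 inability is then scored at the worst value, and a loss that happened during 205MS301 or in the gap before entry appears as decline in 205MS303. If there is no earlier value, the subject has no change score.

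MSFC change and PASAT 3 change are listed secondary endpoints, and the effect of switching from IFN beta-1a is a secondary objective (SAP 1.2). Change from 205MS303 entry by former arm bears directly on that objective. If one arm lost more function before entry, the distortion would differ between arms.

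**Working it through.** **1. The SAP's own figure.** The back-calculated raw walk score is R = MEAN + 13.7 × SD. Put into Z = -(R - MEAN)/SD it returns -13.7 for any mean and SD. With MEAN 6 and SD 2, for example, R = 33.4 and Z = -(33.4 - 6)/2 = -13.7. The figure reproduces.

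**2. Weight in the composite.** MSFC z is the mean of three component z-scores, so a walk z of -13.7 contributes -13.7/3 = -4.57.

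**3. One subject, unable to walk the test at entry and unchanged afterwards.** Let z0 be the last measured walk z before entry.

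| Reading of the SAP | 205MS303 walk baseline | Walk change | Composite change |
|---|---|---|---|
| Inability scored at entry, or an already scored value counts as available | -13.7 | 0 | 0 |
| Entry not scored, earlier measured value used | z0 | -13.7 - z0 | (-13.7 - z0)/3 |
| Entry not scored, no earlier value | none | none | none |

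The SAP does not give z0. Over an assumed range:
- z0 = 0: walk change -13.7, composite -4.57.
- z0 = -1: walk change -12.7, composite -4.23.
- z0 = -3: walk change -10.7, composite -3.57.

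The true change is 0 in each case.

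**4. PASAT 3.** The reference mean and SD are not in the SAP. Assuming a mean of 45 to 50 and an SD of 8 to 13, a raw score of 0 has z from -45/13 = -3.46 to -50/8 = -6.25. For a subject previously at the reference mean, that is -1.15 to -2.08 on the composite.

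**5. Effect on a group mean (walk).** The shift is share affected × (-13.7 - z0)/3. The share is not in the SAP.
- Assumed 0.25%, z0 = -3: 0.0025 × -3.57 = -0.009.
- Assumed 2%, z0 = 0: 0.02 × -4.57 = -0.091.

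For scale, assume 600 subjects per former arm (half of the approximately 1200 in SAP section 2), z0 = 0, and an SD of change of 0.4 to 0.5 without the affected subjects. Those subjects also inflate the variance, so the SD is √(s² + p(1 - p) × 4.57²).
- 3 subjects (0.5%): shift -0.023. SD 0.51 to 0.59, standard error 0.021 to 0.024. The shift is about 1 standard error.
- 6 subjects (1%): shift -0.046. SD 0.61 to 0.68, standard error 0.025 to 0.028. The shift is about 1.7 to 1.9 standard errors.

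**The case against.** The strongest reply is that the bias is inferred and not written.

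- **The no-imputation sentence stands under PASAT 3 only.** A reader might infer that 8.4.3 bars baseline scoring for every component. It does not. For walk and 9HPT, the both-trials rules are worded for post-baseline visits, and the one-trial rules name baseline before excluding it. There the fault is an open and contradictory rule. This stands.
- **Misdating is not inevitable.** A reader might infer that every subject unable at entry is charged with a false decline. Section 5.2.1 says latest available value. It does not say latest completed test. Late 205MS301 visits and the entry test are post-baseline to 205MS301, so they may already carry the worst score. If that score counts as available, change is 0. This stands as a possible reading, but the SAP does not choose it.
- **Few lose their change score.** That outcome requires no earlier usable value, and these subjects completed 205MS301. They would still contribute post-baseline actual values. This stands.
- **Section 7.12.** A reader might infer that subjects too impaired for PASAT 3 certainly vanish from the standalone summary. The default in 5.4 yields where something else is specified, and the zero in 8.4.3 is a raw PASAT 3 score, the quantity that 7.12 summarises. This is mainly a missing cross-reference.
- **Outside algorithm.** The imputation follows an MSFC algorithm that is not reproduced in the SAP, and it may treat baseline in its own way. That does not tell the programmer which baseline is meant when there are two.

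**Conclusion.** The point holds in a limited form. The asymmetry is in the text: explicit for PASAT 3, and carried by the both-trials-missing wording for walk and 9HPT. With a second baseline defined as the latest available value, the direct reading can give a wrong change score, and the SAP does not settle which reading applies.

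Per affected subject, the false composite change is about -3.6 to -4.6 for the walk, resting on an assumed prior z of -3 to 0. The number affected cannot be known from the SAP, so the group shifts shown are illustrations.

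Four things limit the reach. The summaries are descriptive. MSFC in 205MS303 is scheduled only at Weeks 0, 12, 24 and 48. The Combined Study Period analysis scores any inability that arises after the 205MS301 baseline, so it is largely unaffected. The primary safety endpoints are not touched. The documents do not support a claim that the 205MS303 MSFC results are biased as a matter of fact, or in a known direction between the former arms.

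**What to change.** In SAP 8.4.3:
1. Limit the sentence on not imputing missing baseline values to the 205MS301 baseline.
2. State that disability-related inability at the 205MS303 entry test, or at the last 205MS301 test used in its place, is scored by the post-baseline rule for all three components, and that this scored value is the 205MS303 baseline.
3. Rewrite the one-trial rules for walk and 9HPT so that the lead-in and the condition name the same visits.

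In SAP 7.12, state that the PASAT 3 zero rule applies to post-baseline visits and to the 205MS303 baseline.

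In the outputs, report by former arm how many subjects had a worst score assigned at 205MS303 entry and how many had no change score.

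The cost is a few lines of text and one derivation rule, with no new data. The downside is that a subject at the worst score at entry cannot show further decline on that component. The test could not measure any further decline in that subject in any case.

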MRI endpoints at selected visits of the 2015MS301 and 2015MS303 studies: 1) total number of new or newly-enlarging T2 hyperintense lesions 2) total number of new T1 hypointense lesions 3) total number of Gd lesion 4) total volume of T2 hyperintense lesions 5) the volume of new or newly enlarging T2 lesions 6) total volume of new T1 hypointense lesions 7) Percent Brain Volume Change (PBVC)	205MS301-303 ITT population	205MS301 Treatment Period	205MS301 Baseline	Descriptive statistics by previous treatment group in 205MS301 and by study visit in 205MS301 study. For the total number of new or newly enlarging T2 lesions and the total number of new T1 lesions: negative binomial model, adjusted for 301 baseline characteristics.
	205MS301-303 ITT population	205MS303 Treatment Period	205MS303 Baseline	Descriptive statistics by previous treatment group in 205MS301 and by study visit in 205MS303 study. For the total number of new or newly enlarging T2 lesions and the total number of new T1 lesions: negative binomial model, adjusted for 303 baseline characteristics. PBVC will be analyzed during the 205MS303 treatment period and with either 205MS301 or 205MS303 baseline.
EDSS: actual score and change from baseline	205MS301-303 ITT population	205MS303 Treatment Period	205MS303 Baseline	Descriptive statistics by previous treatment group in 205MS301 and by study visit in 205MS303.
MSFC z-score and component z-scores: actual value and change from baseline	205MS301-303 ITT population	Combined Study Period	205MS301 Baseline	Descriptive statistics by previous treatment group in 205MS301 and by study visit in 205MS301 and 205MS303. See section 8.4.3.
		205MS303 Treatment Period	205MS303 Baseline	Descriptive statistics by previous treatment group in 205MS301 and by study visit in 205MS303. See section 8.4.3.
PASA 3: actual value and change from baseline	205MS301-303 ITT population	Combined Study Period	205MS301 Baseline	Descriptive statistics by previous treatment group in 205MS301 and by study visit in 205MS301 and 205MS303.

**Protocol 205MS303
Statistical Analysis Plan**

Final Version 1.0

Endpoint	Population	Study/Treatment Period	Baseline	Statistical Methods
		205MS303 Treatment Period	205MS303 Baseline	Descriptive statistics by previous treatment group in 205MS301 and by study visit in 205MS303.

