8.4.3. MSFC Score

There are 3 components to the MSFC:

- (1) the average scores from the 4 trials on the 9-hole peg test (9HPT) (the 2 trials for each hand are averaged, converted to the reciprocals of the mean times for each hand and then the 2 reciprocals are averaged);
- (2) the average scores of the 2 Timed 25-Foot Walk trials;
- (3) the number correct on the Paced Auditory Serial Addition (PASAT) 3 test.

The MSFC z-score is calculated by creating z-scores for each component of the MSFC, as explained below, and averaging them to create an overall composite score, i.e.,

MSFC z-score = $(Z_{25\text{-foot-walk}} + Z_{9\text{HPT}} + Z_{\text{PASAT}3})/3$, where Z_{xxx} refers to Z-scores.

	
Protocol 205MS303 Statistical Analysis Plan
	
Final Version 1.0

---	--	--

A z-score represents the number of standard deviations a subject's test result is higher ($z > 0$) or lower ($z < 0$) than the average test result ($z = 0$) of the reference population.

Calculation for Raw and Z-score for each component

The following describes the scoring, rules for missing value imputation for each component.

Timed 25-Foot Walk Z-score Calculation

The Z-score is calculated as in the following formula:

$$Z_{25\text{-foot-walk}} = (-1) * \frac{((t_1 + t_2) / 2) - MEAN(reference)}{SD(reference)},$$

where t_1 and t_2 are the time (in seconds) from the two trials, and the mean (reference) and SD (reference) are the mean and standard deviation respectively, of baseline values for the reference population. For scores to be comparable with scores in 205MS301, the same reference population is used. Baseline values for the reference population are the values at the 205MS301 baseline for the reference population (205MS301 ITT population). The same is applicable to 9HPT and PASAT 3 Z-scores.

Timed 25-Foot Walk Raw Score Calculation

The row score is calculated as in the following formula:

$$R_{25\text{-foot-walk}} = (t_1 + t_2) / 2,$$

where t_1 and t_2 are the time (in seconds) from the two trials.

Missing Value Handling for Timed 25-Foot Walk

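### MSFC scoring: percentage change of z-scores has no usable meaning, and the 9HPT rule for a hand that cannot be tested is either wrong for one lost hand or silent on it

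*SAP*

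**What the plan says.** **Percentage change.** For the Combined Study Period, Section 8.4.3 plans "actual value, change and percentage change from the 205MS301 baseline in the MSFC z-scores as well as for each individual MSFC component z-scores". The next sentence, for the 205MS303 Treatment Period, asks for change only. Table 8 in Section 7.1 covers both periods and describes the endpoint as "MSFC z-score and component z-scores: actual value and change from baseline". Section 8.4.3 fixes the scale: a score is higher or "lower ($z < 0$) than the average test result ($z = 0$) of the reference population", and "Baseline values for the reference population are the values at the 205MS301 baseline for the reference population (205MS301 ITT population").

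**9HPT.** The two trials of each hand are averaged, then "converted to the reciprocals of the mean times for each hand and then the 2 reciprocals are averaged". If a single trial is missing because of a physical limitation, "the score for that specific trial will be imputed with a raw score value of 777, and then the average of the two trials will" enter the usual formula. A further rule begins "If both scores from either hands are missing for any post-baseline visit, due to MS related physical limitation or other physical limitations". In that case the subject receives a raw score of 777 and Z = (1/777 - mean)/SD. The 9HPT carries one third of the MSFC.

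**The concern.** A percentage change needs a denominator with a fixed sign and a true zero. A z-score has neither. Here the reference baseline that sets the zero is the same visit that supplies the denominator, so small and negative denominators are built in. A secondary endpoint would carry a column whose sign does not track benefit.

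The second 9HPT rule places one value on the whole subject, and its formula has no term for the other hand. If it is triggered by one hand alone, a valid measurement is thrown away and the result contradicts the averaging formula of the same section. If it is meant only for both hands, programmers have no explicit instruction for a subject who can use one hand.

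**Working it through.** The SAP states no figure to reproduce on this point. Its own formulas are used.

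**Part 1: percentage change = 100 × (follow-up z - baseline z) / baseline z**

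| Baseline z | Follow-up z | Change | Percentage |
|---|---|---|---|
| 1.0 | 1.2 | +0.20 | +20% |
| 0.1 | 0.3 | +0.20 | +200% |
| 0.01 | 0.21 | +0.20 | +2000% |
| 0 | 0.2 | +0.20 | undefined |
| -0.01 | 0.19 | +0.20 | -2000% |
| -1.0 | -0.8 | +0.20 | -20% |
| -1.0 | -1.2 | -0.20 | +20% |

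The same improvement takes any size and either sign, and a worsening can read as positive. Dividing by the absolute baseline would repair the sign but not the instability: ±0.01 still gives 2000%.

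As an illustration, 600 subjects were simulated 2000 times. Assumptions: baseline z normal with mean 0 and SD 1.0, true mean change +0.10, SD of change 0.3. The mean percentage change lay between -369% and +400% in 95% of runs, and about 50% of improvers had a negative percentage. The mean absolute change had a standard error of 0.012. With baseline SD 0.7 or SD of change 0.5 the range of the mean percentage was wider.

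**Part 2: 9HPT**

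Inputs from the SAP: the value 777, averaging of the two hands' reciprocals, and the one-third weight in the composite. Assumed, because the SAP does not give them: reference mean reciprocal 0.05 per second, SD 0.010 (range 0.008 to 0.012), and 20 s for an intact hand (range 18 to 30 s).

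With 20 s, mean 0.05 and SD 0.010:

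- Nothing lost: (1/20 - 0.05)/0.010 = 0.00.
- One trial lost: that hand's mean time is (777 + 20)/2 = 398.5 s, so Z = ((1/398.5 + 1/20)/2 - 0.05)/0.010 = -2.37.
- One hand lost, averaging formula with 777 for that hand: ((1/777 + 1/20)/2 - 0.05)/0.010 = -2.44.
- One hand lost, literal rule: (1/777 - 0.05)/0.010 = -4.87.
- Both hands lost: (1/777 - 0.05)/0.010 = -4.87, the same value.

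The raw score for one lost hand is (777 + 20)/2 = 398.5 s by averaging and 777 s by the literal rule.

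The error in the composite under the literal reading is (1/t - 1/777)/(2 × SD)/3, where t is the intact hand's mean time. The reference mean cancels.

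- t = 20 s, SD 0.010: (0.05000 - 0.00129)/0.060 = 0.81.
- t = 18 s, SD 0.008: (0.05556 - 0.00129)/0.048 = 1.13.
- t = 30 s, SD 0.012: (0.03333 - 0.00129)/0.072 = 0.45.

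When both hands were equally fast before the loss, the literal rule exactly doubles the fall in Z, whatever the time and SD.

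**The case against.** **The 9HPT phrase is ambiguous.** A reader might infer that the SAP definitely scores one lost hand as two. The wording leans that way: two hands have four trials, so two scores point to one hand, and the preceding paragraph uses *either* to mean one hand or the other. But the phrase is ungrammatical and may have been meant as both hands. On that reading the formula agrees with the averaging rule, since (1/777 + 1/777)/2 = 1/777 and (777 + 777)/2 = 777. The SAP also defers to the MSFC manual, which is not available here. This objection stands. What survives is that the sentence either discards valid data or leaves one-hand loss without an explicit rule.

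**The step between one and two lost trials.** A reader might infer that one failed trial costs little and that the whole penalty falls on the second. The figures do not support this: the first already takes Z from 0.00 to -2.37. The defect is that a second lost trial in the same hand should add about 0.06, but under the literal rule it adds about 2.50.

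**The simulation assumes mean-zero baselines.** The analysed subjects are 205MS301 completers who went on to receive DAC HYP in 205MS303, not the whole reference population, so neither a mean of exactly zero nor a 50% negative share is given by the SAP. A median would not explode as a mean does. The sign reversal needs none of these assumptions, and with baselines symmetric about zero and independent of the change, the median percentage is zero whatever the true gain.

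**The consequence is limited.** The primary endpoints are AEs and SAEs. MSFC is one of many secondary endpoints and is summarised descriptively. In 205MS303 it is scheduled only at baseline and Weeks 12, 24 and 48. This stands and lowers the severity.

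**Conclusion.** The percentage change is wrong as written. This follows from the SAP's definitions alone, and Table 8 already omits it. The simulated spread is illustrative; the sign reversal and the absence of any bound are certain.

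The 9HPT sentence must be rewritten on either reading. Under the literal one, the composite for an affected subject is too low by about 0.45 to 1.13, conditional on the assumed SD and intact-hand times. How many subjects are affected is unknown; the rule applies only where trials are missing because of physical limitation.

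Severity is moderate. A reader might infer that the MSFC results as a whole would be invalid. The SAP does not support that: actual value and absolute change are also reported and are untouched by the percentage problem, and the second problem reaches only a subset of subjects.

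**What to change.** 1. In Section 8.4.3, delete the percentage change for the MSFC and component z-scores. Report actual value and absolute change, as Table 8 does. Do not replace it with a percentage on raw times that include imputed values: one 20 s hand lost moves the raw score from 20 to 398.5 s, which is (398.5 - 20)/20, or about +1,890%.
2. Rewrite the 9HPT rule. When both trials of one hand are missing because of physical limitation, set that hand's mean time to 777 and use Z = ((1/777 + 1/mean time of the other hand)/2 - mean)/SD, with the raw score averaged in the same way. Keep Z = (1/777 - mean)/SD and raw score 777 for loss of both hands only.

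The cost is two wording changes and one derivation. One uninterpretable table column is lost, and no new data are needed.
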